**Table 3. Population Overview at Proposed Clinical Sites**

	Penn State Hershey	Pitt/UPMC	TUHS	Hopkins	University of Utah
EHR platform	Cerner	Cerner (inpatient) Epic (outpatient)	Epic	Epic	Epic
Distinct patients with at least one encounter or record in EHR	615,012	5,537,583	457,388	4,800,000	1,602,245
Active patients with data in EHR	520,310	1,880,457	323,682	1,764,221	581,568

**PaTH Patient Population.** The patients in the PaTH network are diverse—22% are aged 17 years or younger and 20% are aged 65 years or older. Over 25% are non-white and 20% have public insurance (excluding Medicare) or no insurance. The organizations are also diverse with many affiliated community-based hospitals and outpatient practices in addition to their academic hospitals. Other facilities include rehabilitation hospitals, dialysis centers, fitness and wellness centers, psychiatric hospitals, ambulatory surgery centers, and home healthcare support.

**PaTH Data Sources.** PaTH leverages health-related data from: 1) electronic health records (EHR), 2) patient-reported outcomes (PROs), 3) insurance claims data, and 4) biospecimen data. The PaTH data that will be used in the proposed work will be limited to EHR data and claims data.

**PaTH Governance and Regulatory Issues.** A significant challenge of multi-institutional research networks is managing the governance and regulatory issues that arise when different institutions have their own procedures for conducting research and managing their clinical health records. Perhaps the largest tasks to date for the PaTH CDRN have been the establishment of several governance policies that were required in order for the network to function.

Thus, the proposed research not only builds on the PaTH data infrastructure, but also on its established governance and regulatory policies. The most important agreements that have been executed are: 1) the PaTH network's **data use agreement (DUA)** and the 2) PaTH network's **reliance agreement for a central Institutional Review Board (IRB)** to oversee the protection of human subjects. The PaTH DUA establishes a secure environment for sharing and handling patient data for the purposes of research within the PaTH network. These policies describe data standardization, data privacy standards, and sharing of data within the CDRN. Under the PaTH DUA, we will be able to conduct the research described in this proposal without delays due to need to establish such agreements.

The PaTH network has also established a centralized process for IRB reviews. Creating separate IRB protocols with different formats and procedures to be reviewed by separate IRBs would be an inefficient and ineffective process. This problem has been recognized by the National Institutes of Health (NIH), who is promoting the use of a single IRB in multi-site clinical research studies to reduce duplication of effort, speed-up the initiation of important research, and save time and resources. To this end, the PaTH network has established a reliance agreement naming Johns Hopkins IRB as our central IRB of record. Under the reliance agreement, the other institutions agree to allow the Johns Hopkins IRB to review the study protocol, and to honor the approval of the protocol. To ensure that each PaTH institution would have input into the review process, we convened the PaTH Network Protocol Review Committee, or PNPRC. Two IRB members from each institution serve on the PNPRC, an IRB member and a community member, currently totaling 8 members. Only after the PNPRC approves a PaTH protocol, does it then get submitted to the Johns Hopkins IRB for centralized review.

### **2.3 Study Rationale**

The proposed project is significant for several reasons. First, diabetes is a leading public health concern and associated with significant economic burden. Recent health policies changes (e.g., CMS coverage) are expected to impact diabetes and pre-diabetes outcomes and the proposed project will capture differences in these outcomes through a broad region. Understanding the uptake of the CMS weight counseling benefit and its effect on diabetes and pre-diabetes outcomes can inform future policies to improve overall care for patients.

## **3.0 Inclusion and Exclusion Criteria**

### **3.1 Inclusion Criteria**

#### **Patients with Diabetes**

- Ages 18 and older
- Indication of Type 2 Diabetes as defined using a clinically validated algorithm: type 2 diabetes mellitus on the problem list, diabetes-specific medications, hemoglobin A1c (HbA1c) results > 7.0%, or one inpatient diagnosis code or two out-patient diagnosis codes for type 2 diabetes (ICD-9 codes 250.xx)
- patients who have either: (1) had at least 2 outpatient primary care visits in one of the PaTH health systems in the past 3 years (since January 1, 2012), or (2) for whom claims data are available

#### **Patients with Pre-Diabetes (At risk):**

- Ages 18 and older
- BMI  $\geq 25 \text{ kg/m}^2$
- patients who have either: (1) had at least 2 outpatient primary care visits in one of the PaTH health systems in the past 3 years (since January 1, 2012), or (2) for whom claims data are available

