### **3.2 Exclusion Criteria**

- Patients under the age of 18

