***At-risk Cohort Definition.*** The cohort of patients under study will be defined as patients age 18 and older who are at risk for the development of diabetes, based on being overweight. Patients seen at one of the four PaTH institutions will be included in the at-risk cohort if they have a  $BMI \geq 25 \text{ kg/m}^2$ , based on most recent recorded weight and at least one recorded height. The at-risk cohort will be further limited to patients who will likely to be captured in the PaTH EHR records or claims data so that outcome assessments can occur. Thus, we will further limit the at-risk cohort to patients who have either: (1) had at least 2 outpatient primary care visits in one of the PaTH health systems in the past 3 years (since January 1, 2012), or (2) for whom claims data is available. The cohort will be dynamic, with new patients added into the cohort after 2015 as they meet the at-risk cohort definition prospectively. Patients will not be removed from the cohort, even if they are no longer overweight. The observational period for the outcome variables will be for the 10-year period from 2009-2019, thus including 3 years of data prior to the first policy change (CMS instituting coverage for intensive behavioral therapy for obesity) and 3 years after the last policy change (Pennsylvania Medicaid expansion) under study.

[figure not shown]
intensive behavioral therapy for obesity) and 3 years after the last policy change (Pennsylvania Medicaid expansion) under study.

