**Table 1. Proposed Outcomes for the Pre-diabetes and Diabetes Cohorts**

Outcomes	Definition	Notes
Pre-diabetes cohort		
Weight loss during counseling	Weight lost from first IBT visit to final IBT visit	Available at all PaTH sites
Weight loss maintenance	% of weight lost during program and maintained over remaining time period, reported by year	Available at all PaTH sites
Diabetes incidence	% of patients who develop diabetes per year following weight counseling	Available at all PaTH sites
Patient-reported outcomes	-SF-12 -PHQ-2, PHQ-8, PHQ-9 -Physical function -sleep -fruit and vegetable consumption -social support -physical activity -PROMIS (PROMIS 29, physical function, depression) -healthy lifestyles -patient reported medication reconciliation	Available at some sites – Formal inventory of PROs will be collected at each institution at the beginning of the project, to be included as secondary outcomes
Diabetes cohort		
Weight loss during counseling	Weight lost from first IBT visit to final IBT visit	Available at all PaTH sites
Weight loss maintenance	% of weight lost during program and maintained over remaining time period, reported by year	Available at all PaTH sites
Patient reported outcomes	-SF-12 -PHQ-2, PHQ-8, PHQ-9 -Physical function -sleep -fruit and vegetable consumption -social support -physical activity -PROMIS (PROMIS 29, physical function, depression) -healthy lifestyles -patient reported medication reconciliation	Available at some sites – Formal inventory of PROs will be collected at each institution at the beginning of the project, to be included as secondary outcomes
Uncontrolled diabetes	Average A1c > 9 or no A1c	Available at all PaTH sites
Controlled blood pressure	SBP < 140, DBP < 90, averaged across values over year	Available at all PaTH sites
On a statin medication	Evidence of a statin medication on current EHR medication list	Available at all PaTH sites
Receiving annual eye exam	Documentation of eye exam once in past year	Available at all PaTH sites
Receiving annual urinary microalbumin test	Documentation of lab testing for urinary microalbumin at least once in past year	Available at all PaTH sites
Lower extremity amputations	Documentation of procedure for lower extremity amputation or billing code through health plans in past year	Available at all PaTH sites

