Diabetes Service Use	-Clinic visit with primary or secondary diagnosis of diabetes -Emergency department visit with primary or secondary diagnosis of diabetes -Hospitalization with primary or secondary diagnosis of diabetes	Available at all PaTH sites
Exposure variables		
Individual level	-Sociodemographics (e.g., age, sex, race, insurance status, rural vs. urban) -Medical co-morbidities	Available at all PaTH sites
Provider/practice level	-Practitioner type (advanced practice vs. MD/DO) -Practitioner specialty -Practice size (# of providers) -Practice type (multispecialty, academic) -Practice setting (rural vs. urban)	To be determined

**Data Transfer.** The PaTH network has established an operational data infrastructure with the necessary technical safeguards as agreed upon in the PaTH Data Use Agreement (DUA) for sharing and analyzing data while addressing data confidentiality and security concerns. PaTH has deployed two mechanisms for storing, protecting, and sharing data (as described previously under PaTH Governance and Regulatory Issues): (1) data with PHI are stored and protected behind each institution's firewall in the distributed data network and (2) de-identified data are sent to the PaTH data center at

the University of Pittsburgh (CERC-DC). Once data integration is accomplished at each site, sites will remove all PHI and send the de-identified version of the integrated data to the CERC-DC through PaTH's virtual private network/secure file transfer protocol (VPN) which has been operational for data transmission since November 2014. Data analysis can then be performed via secure remote computing using standard statistical software packages (e.g., SAS). This model ensures that the highest level of privacy and confidentiality for the data that are maintained at each site, the CERC-DC, and at Penn State.

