Furthermore, we will use the similar models as described above to evaluate post-policy impact of obesity screening and counseling (number of visits) on the outcomes such as weight loss, diabetes incidence, and diabetes outcomes (including hemoglobin A1c, controlled blood pressure, use of a statin medication). The outcome data collected after the universal coverage change (i.e.,  $t = 0, 1, \dots, 6$ ) will be used to estimate the trend of change. The number of screening and counseling will be used as a predictor in the mixed effects models. The effects of patient and practice characteristics will also be examined in the models. Statistical software SAS 9.4 and R environment will be used to implement the proposed analyses.

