## Propensity scores matching

In the proposed modeling framework above, we adjust for the subject-level and cluster-level differences by including the exposure variables at different levels as covariates in the models. We also will consider a secondary analysis with a propensity scores matching approach to adjusting for these differences. A wide array of patient measures in the EHR, including demographics, insurance coverage, medical co-morbidities, health behaviors, and information on use of health care services, will be used to calculate the propensity scores. Propensity score-based stratification analysis will be performed to evaluate the overall impact of health policy using the modeling framework similar to that described above.

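### The at-risk cohort has no glycaemic entry criterion and no baseline A1c covariate is specified, so diabetes incidence by counseling is left open to confounding by baseline glycaemia

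*Combined protocol and SAP*

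**What the plan says.** **Cohort.** Section 3.1 lists three entry criteria under "Patients with Pre-Diabetes (At risk": adult age, BMI of at least 25, and either two primary care visits or available claims data. Section 7.2 describes these patients as people "who are at risk for the development of diabetes, based on being overweight". The sole exclusion in Section 3.2 is "Patients under the age of 18". No A1c or glucose criterion appears.

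**Case definition.** Sections 3.1 and 7.2 classify a patient as diabetic by any one of several routes: a problem-list entry, a diabetes drug, "hemoglobin A1c (HbA1c) results > 7.0" percent, one inpatient code, or two outpatient codes.

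**Outcome and comparison.** Table 1 gives the pre-diabetes cohort the outcome diabetes incidence, the percentage "of patients who develop diabetes per year following weight counseling". Aim 2 in Section 1.0 contrasts patients who were counseled with those who were not. For the model, Section 8.0 says: "The number of screening and counseling will be used as a predictor in the mixed effects models". It adds that patient and practice characteristics will be examined.

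**Adjustment.** The individual-level variables in Table 1 are "Sociodemographics (e.g., age, sex, race, insurance status, rural vs. urban") and medical co-morbidities. The propensity score inputs in Section 8.0 are a wide set of EHR measures, "including demographics, insurance coverage, medical co-morbidities, health behaviors, and information on use of health care services". That analysis is meant to evaluate the overall effect of health policy.

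**The concern.** How close a patient already is to the diabetes definition should strongly predict who is later counted as an incident case. It may also influence who is offered counseling, who accepts it, and how many visits follow. A variable linked to both exposure and outcome needs to be in the adjustment set of a non-randomized comparison. Here the cohort is wide on exactly that variable, and the plan does not name it as a covariate.

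If counseled and uncounseled patients differ in baseline glycaemia, the Aim 2 incidence result could hide a preventive effect, invent one, or suggest harm. Section 2.3 expects the study to inform future policy. The size of the cohort does not protect against this, because a large sample makes a biased estimate precise.

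**Working it through.** **1. Where A1c appears.** It has two roles: as one route into the case definition (Sections 3.1 and 7.2), and as an outcome (Aim 2, Table 1, Section 8.0). It is not named as an entry criterion for the at-risk cohort, in the Table 1 exposure variables, in the Aim 2 model, or among the propensity inputs.

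**2. Whether another part of the model covers it.**
- The control for baseline level and trend in Section 8.0 refers to the pre-policy level and slope of the outcome in the segmented model. For incident diabetes every patient at risk starts at zero, so there is no informative baseline level. The Aim 2 model also uses only data from after the coverage change.
- Subject random effects are assumed normal with mean zero. They do not adjust for a baseline variable related to exposure.
- The propensity analysis is secondary and targets policy impact. None is specified for counseled versus uncounseled patients.

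**3. Document figure.** The at-risk site counts reproduce the stated total: 167,799 + 950,020 + 471,860 + 212,314 + 260,506 = 2,062,499.

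**4. Possible size of the bias.** The plan gives no incidence, no A1c distribution and no counseling uptake, so every input here is an assumption. Let the true counseling effect be null. Let pu and pc be the proportions near diagnosis among uncounseled and counseled patients, and let R be the incidence ratio of the near-diagnosis group to the rest. The crude rate ratio is

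RR = [pc·R + (1 − pc)] / [pu·R + (1 − pu)].

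With pu = 0.30:

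| pc | R = 3 | R = 5 | R = 10 |
|---|---|---|---|
| 0.20 | 1.4/1.6 = 0.88 | 1.8/2.2 = 0.82 | 2.8/3.7 = 0.76 |
| 0.35 | 1.7/1.6 = 1.06 | 2.4/2.2 = 1.09 | 4.15/3.7 = 1.12 |
| 0.40 | 1.8/1.6 = 1.13 | 2.6/2.2 = 1.18 | 4.6/3.7 = 1.24 |
| 0.50 | 2.0/1.6 = 1.25 | 3.0/2.2 = 1.36 | 5.5/3.7 = 1.49 |

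A second set of assumptions keeps pu = 0.30 and takes pc from 0.45 to 0.60:
- Annual incidence 5% versus 1%: uncounseled 0.30×5 + 0.70×1 = 2.2%; counseled 0.45×5 + 0.55×1 = 2.8% to 0.60×5 + 0.40×1 = 3.4%. RR = 1.27 to 1.55.
- Annual incidence 4% versus 1.5%: uncounseled 2.25%; counseled 2.625% to 3.0%. RR = 1.17 to 1.33.

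Across both sets the null rate ratio runs from 0.76 to 1.55. Stratifying on baseline status returns 1.00 by construction.

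**5. Sample size.** Take the pc = 0.40 row, 1% annual incidence in the lower-risk group, and a two-sided test at 0.05. If 1% of the cohort is counseled, the chance of a significant result with no true effect is 0.62, 0.96 and about 1.00 for R = 3, 5 and 10. If 0.1% is counseled, it is 0.12, 0.25 and 0.57.

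**The case against.** Several stronger readings are tempting, and the documents do not support them.

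- **A reader might infer that baseline A1c almost mechanically determines the outcome.** It does not. The case definition is a list of alternatives, and a patient with an A1c of 6.8% can be classified through a code, a drug or the problem list. The 7.0% ceiling applies only to patients who meet no other criterion, and the plan does not say how many there are.
- **A reader might infer that the bias runs against counseling.** That is plausible if sicker patients are referred, but no A1c distribution by counseling status is given. Section 1.0 ties the benefit to obesity, not glycaemia. If healthier patients take up counseling, the bias flatters it.
- **A reader might infer that A1c is barred from every model.** The covariate lists are open-ended, and a coded pre-diabetes diagnosis could enter as a co-morbidity. The supportable statement is that baseline glycaemia is not pre-specified.
- **A reader might fault the propensity inputs.** They serve the policy question, so their content says little about the counseling comparison. What matters is that this comparison has no propensity score of its own.
- **A reader might treat the pre-diabetes label as an error.** The Section 3.1 heading adds the at-risk qualifier, and Section 1.0 defines high risk by BMI. That is an editorial matter.

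Two further objections stand. The ratios above are crude, and adjustment for age, race and co-morbidity could remove part of an imbalance. The plan also defines no index date for uncounseled patients, so adding baseline A1c takes more than adding a column.

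None of this removes the core point: followed as written, the plan does not commit the analysts to adjusting for a strong predictor of the outcome.

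**Conclusion.** The point holds in a limited form. In the at-risk cohort, the Aim 2 comparisons of diabetes incidence by counseling and by number of visits are left open to confounding by baseline glycaemia. The Aim 1 pre/post policy trend is not in question here.

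Direction and size cannot be derived from the documents. The range of 0.76 to 1.55 rests on assumed shares near diagnosis (30% of uncounseled against 20% to 60% of counseled patients) and assumed incidence ratios of about 2.7 to 10, with no credit for other covariates. At the upper end, a true reduction of 1 − 1/1.55 = 35% would be hidden. At the lower end, a null effect would look like a 24% reduction. This should be corrected before the incidence analysis is run.

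**What to change.** - In Section 8.0, define an index date for both groups: for example, the first counseling visit, and a matched eligible visit date for uncounseled patients.
- In the at-risk incidence model, and in any propensity score built for counseled versus uncounseled patients, add the last A1c before the index date. Use categories set in advance, with not measured as its own category. Restricting to values before the index date avoids adjusting for an A1c that counseling may already have changed.
- Report incidence by counseling within each baseline A1c category.
- Repeat the analysis in patients with a recorded baseline A1c.

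**Cost.** This means revised SAP wording, an index-date rule, one stratified table and one sensitivity analysis. The diabetes algorithm already needs A1c results to detect incident cases, and Table 1 lists its A1c-based outcome as available at all sites, although under the diabetes cohort. The team should confirm that values for at-risk patients reach the analysis file.

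**Downside.** The not-measured group will be large and testing is probably selective, so some confounding will remain, and the tested-only analysis may not represent the whole cohort.

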### **3.2 Exclusion Criteria**

- Patients under the age of 18

## 4.0 Sample Selection

### 4.1 Source of the charts/existing restricted data set

The proposed project will utilize the PaTH Network's existing infrastructure for sharing EHR data across our network. The PaTH Network population represents real-world populations of patients, reducing the likelihood of selection biases that occur with clinical trial data or data from individuals within the same insurance plan. This, in turn, enhances the generalizability of our results. While research records residing at each site will retain identifying information, research records will be de-identified (i.e., personal health information (PHI) will be removed from individual records) prior to making data from the local sites available to Penn State.

*PaTH Patient Population.* The patients in the PaTH network are diverse—22% are aged 17 years or younger and 20% are aged 65 years or older. Over 25% are non-white and 20% have public insurance (excluding Medicare) or no insurance. The organizations are also diverse with many affiliated community-based hospitals and outpatient practices in addition to their academic hospitals. Other facilities include rehabilitation hospitals, dialysis centers, fitness and wellness centers, psychiatric hospitals, ambulatory surgery centers, and home healthcare support.

*PaTH Data Sources.* For this study, we will leverage PaTH's : 1) electronic health records (EHR), 2) patient-reported outcomes (PROs), and 3) insurance claims data.

### 4.2 Identification of subjects/charts/existing data

The University of Pittsburgh is the lead site for the PaTH Network. The overall operations of the PaTH Network are run by the PaTH Steering Committee, which will leverage the data infrastructure, established governance and regulatory policies related to data security, data sharing and human subjects protection of the PaTH Network.

We will use the PaTH Network to identify potential patients who meet our eligibility criteria. PaTH's infrastructure enables and allows for the development, validation, and deployment of electronic algorithms for identifying patients with the conditions of interest. PaTH will continue to follow the guidance of the NIH Health Systems Collaboratory's work on EHR-based phenotyping to create computable phenotypes for the proposed diabetes and pre-diabetes cohorts. Phenotypes will be based on the above inclusion/exclusion criteria.

